### Meningoencephalitis

Immune-related meningoencephalitis is an identified risk associated with the administration of atezolizumab. Immune-related meningoencephalitis should be suspected in any patient presenting with signs or symptoms suggestive of meningitis or encephalitis, including, but not limited to, headache, neck pain, confusion, seizure, motor or sensory dysfunction, and altered or depressed level of consciousness. Encephalopathy from metabolic or electrolyte imbalances needs to be distinguished from potential meningoencephalitis resulting from infection (bacterial, viral, or fungal) or progression of malignancy, or secondary to a paraneoplastic process.

All patients being considered for meningoencephalitis should be urgently evaluated with a CT scan and/or MRI scan of the brain to evaluate for metastasis, inflammation, or edema. If deemed safe by the treating physician, a lumbar puncture should be performed and a neurologist should be consulted.

Patients with signs and symptoms of meningoencephalitis, in the absence of an identified alternate etiology, should be treated according to the guidelines.

### Neurologic disorders

Myasthenia gravis and Guillain-Barré syndrome have been observed with single-agent atezolizumab. Patients may present with signs and symptoms of sensory and/or motor neuropathy. Diagnostic work-up is essential for an accurate characterization to differentiate between alternative etiologies. Management guidelines for neurologic disorders, and specific guidelines for myelitis, are provided in the tables below.

| Event                               | Management   |
|-------------------------------------|--|
| Immune-mediated neuropathy, Grade 1 | 

• Continue atezolizumab.

• Investigate etiology.

• Any cranial nerve disorder (including facial paresis) should be managed as per Grade 2 management guidelines below.

 |

| Event  | Management   |
|--|--|
| Immune-mediated neuropathy, including facial paresis, Grade 2      | 
 
Withhold atezolizumab for up to 12 weeks after event onset.a
 
Investigate etiology and refer patient to neurologist.
 
Initiate treatment as per institutional guidelines.
 
For general immune-mediated neuropathy: 
 
If event resolves to Grade 1 or better, resume atezolizumab.b
 
If event does not resolve to Grade 1 or better while withholding atezolizumab, permanently discontinue atezolizumab.c
 
 
 
For facial paresis: 
 
If event resolves fully, resume atezolizumab.b
 
If event does not resolve fully while withholding atezolizumab, permanently discontinue atezolizumab.c
 
 
 
 |
| Immune-mediated neuropathy, including facial paresis, Grade 3 or 4 | 
 
Permanently discontinue atezolizumab.c
 
Refer patient to neurologist.
 
Initiate treatment as per institutional guidelines.
 
  |
| Myasthenia gravis and Guillain-Barré syndrome (any grade)          | 
 
Permanently discontinue atezolizumab.c
 
Refer patient to neurologist.
 
Initiate treatment as per institutional guidelines.
 
Consider initiation of corticosteroids equivalent to 1–2 mg/kg/day oral or IV prednisone.
 
   |

a Atezolizumab may be withheld for a longer period of time (*i.e.*, >12 weeks after event onset) to allow for corticosteroids (if initiated) to be reduced to the equivalent of ≤10 mg/day oral prednisone. The acceptable length of the extended period of time must be based on an assessment of benefit–risk by the investigator and in alignment with the protocol requirements for the duration of treatment and documented by the investigator.

b If corticosteroids have been initiated, they must be tapered over ≥1 month to the equivalent of ≤10 mg/day oral prednisone before atezolizumab can be resumed.

c Resumption of atezolizumab may be considered in patients who are deriving benefit and have fully recovered from the immune-mediated event. The decision to re–challenge patients with atezolizumab should be based on investigator's assessment of benefit–risk and documented by the investigator (or an appropriate delegate).

| Event                             | Management   |
|-----------------------------------|--|
| Immune-mediated myelitis, Grade 1 | 
 
Continue atezolizumab unless symptoms worsen or do not improve.
 
Investigate etiology and refer patient to a neurologist.
 
  |
| Immune-mediated myelitis, Grade 2 | 
 
Permanently discontinue atezolizumab.
 
Investigate etiology and refer patient to a neurologist.
 
Rule out infection.
 
Initiate treatment with corticosteroids equivalent to 1–2 mg/kg/day oral prednisone.
 
 |

| Event                                     | Management  |
|---|---|
| Immune-mediated myelitis,
Grade 3 or 4 | 

Permanently discontinue atezolizumab.

Refer patient to a neurologist.

Initiate treatment as per institutional guidelines.

 |

For recommendations to hold atezolizumab and CDX-1127 (varlilumab) and begin corticosteroid treatment, use the following guidance for tapering the corticosteroid and resuming atezolizumab and CDX-1127 (varlilumab) therapy after resolution of the event:

- Corticosteroids must be tapered over  $\geq 1$  month to  $\leq 10$  mg/day oral prednisone or equivalent before atezolizumab and CDX-1127 (varlilumab) can be resumed.
- Atezolizumab and CDX-1127 (varlilumab) may be held for a period of time beyond 12 weeks to allow for corticosteroids to be reduced to  $\leq 10$  mg/day oral prednisone or equivalent.

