## 7. DOSING DELAYS/DOSE MODIFICATIONS

### 7.1 CDX-1127 (varlilumab) and Atezolizumab (all participants)

#### 7.1.1 General AE Management and Dose Modification Guidelines

Dosing of both CDX-1127 (varlilumab) and atezolizumab is fixed with no dose-modification permitted. Both CDX-1127 (varlilumab) and atezolizumab should always be administered on the same day. Monotherapy with atezolizumab or CDX-1127 (varlilumab) alone is not permitted.

On cycle 1 day 1 (first dose), patients will be observed for at least 4 hours after the last study drug administration to monitor for infusion reaction/cytokine release syndrome/hypersensitivity reaction. For all subsequent doses/cycles, patients should be monitored for at least 1 hour following the last administration of study drug. Infusions should be given in a monitored setting that has ready access to an intensive care unit in case of a severe infusion reaction.

Acetaminophen may be used to manage drug-related adverse events such as fever, myalgias or arthralgias and anti-histamines may be used to manage drug-related adverse events such pruritus.

Patients may temporarily suspend study treatment for up to 84 days (12 weeks) beyond the scheduled date of delayed infusion if study drug-related toxicity requiring dose suspension is experienced. If atezolizumab and CDX-1127 (varlilumab) are held because of AEs for >84 days beyond the scheduled date of infusion, the patient will be discontinued from atezolizumab-CDX-1127 (varlilumab) and will be followed for safety and efficacy as specified in this protocol. If the AE resolves within 84 days and the patient is receiving corticosteroid therapy for the event, atezolizumab-CDX-1127 (varlilumab) may be held for longer than 84 days (up to 4 weeks) in order to allow tapering of the steroid dose to  $\leq 10$  mg oral prednisone or equivalent.

Dose interruptions for reasons other than toxicity, such as surgical procedures, may be allowed. The acceptable length of interruption will be at the discretion of the study PI in consultation with CTEP.

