| Meningo-encephalitis, immune-related (signs and symptoms in absence of an identified alternate etiology) | All grades | 
Permanently discontinue atezolizumab & CDX-1127 (varlilumab). Patient may not resume treatment, regardless of benefit.
 
Refer patient to neurologist
 
Initiate treatment with 1–2 mg/kg/day IV methylprednisolone or equivalent and convert to 1–2 mg/kg/day oral prednisone or equivalent upon improvement.
 
If event resolves to grade 1 or better, taper corticosteroids over <math>\geq 1</math> month.
 
If event does not
 | 
Permanently discontinue atezolizumab & CDX-1127 (varlilumab) and cobimetinib. Patient may not resume treatment with atezolizumab & CDX-1127 (varlilumab) and cobimetinib, regardless of benefit.
 
Refer patient to neurologist
 
Initiate treatment with 1–2 mg/kg/day IV methylprednisolone or equivalent and convert to 1–2 mg/kg/day oral prednisone or equivalent upon improvement.
 
If event resolves to grade 1 or better, taper corticosteroids over <math>\geq 1</math> month.
 |
|--|------------|--|---|

|   |            |   |  |
|---|------------|---|--|
|   |            | improve within 48 hours after initiating corticosteroids, consider adding an immunosuppressive agent.   | month.

If event does not improve within 48 hours after initiating corticosteroids, consider adding an immunosuppressive agent.  |
| Myasthenia gravis and Guillain-Barré syndrome | All grades | Permanently discontinue atezolizumab & CDX-1127 (varlilumab).
Patient may not resume treatment, regardless of benefit.

See Section 7.1.2 for further instructions. | Permanently discontinue atezolizumab & CDX-1127 (varlilumab) and cobimetinib. Patient may not resume treatment with atezolizumab & CDX-1127 (varlilumab) and cobimetinib, regardless of benefit.

See Section 7.1.2 for further instructions. |
| Myocarditis (immune-related)                  | Grades 2-4 | Permanently discontinue atezolizumab and CDX-1127 (varlilumab) and contact the study PI. See Section 7.1.2 for further instructions.  | Permanently discontinue atezolizumab and CDX-1127 (varlilumab) and cobimetinib contact the study PI. See Section 7.1.2 for further instructions.   |
|   |            |   |  |

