  - Dosing interruptions  $>6$  weeks that occur for non-drug-related reasons may be allowed if approved by the Principal Investigator.
  - Prior to re-initiating treatment in a subject with a dosing interruption lasting  $>6$  weeks, the Principal Investigator must be consulted.

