#### **10.3.2 Distribution of Adverse Event Reports**

CTEP-AERS is programmed for automatic electronic distribution of reports to the following individuals: Principal Investigator and Adverse Event Coordinator(s) (if applicable) of the Corresponding Organization or Lead Organization, the local treating physician, and the Reporter and Submitter. CTEP-AERS provides a copy feature for other e-mail recipients.

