**FDA REPORTING REQUIREMENTS FOR SERIOUS ADVERSE EVENTS (21 CFR Part 312)**

**NOTE:** Investigators **MUST** immediately report to the sponsor (NCI) **ANY** Serious Adverse Events, whether or not they are considered related to the investigational agent(s)/intervention (21 CFR 312.64)

An adverse event is considered serious if it results in **ANY** of the following outcomes:

- 1) Death
- 2) A life-threatening adverse event
- 3) An adverse event that results in inpatient hospitalization or prolongation of existing hospitalization for  $\geq 24$  hours
- 4) A persistent or significant incapacity or substantial disruption of the ability to conduct normal life functions
- 5) A congenital anomaly/birth defect.
- 6) Important Medical Events (IME) that may not result in death, be life threatening, or require hospitalization may be considered serious when, based upon medical judgment, they may jeopardize the patient or subject and may require medical or surgical intervention to prevent one of the outcomes listed in this definition. (FDA, 21 CFR 312.32; ICH E2A and ICH E6).

**ALL SERIOUS** adverse events that meet the above criteria **MUST** be immediately reported to the NCI via electronic submission within the timeframes detailed in the table below.

| Hospitalization                                | Grade 1 Timeframes | Grade 2 Timeframes | Grade 3 Timeframes | Grade 4 & 5 Timeframes  |
|--|--------------------|--------------------|--------------------|-------------------------|
| Resulting in Hospitalization $\geq 24$ hrs     |                    | 10 Calendar Days   |                    | 24-Hour 5 Calendar Days |
| Not resulting in Hospitalization $\geq 24$ hrs | Not required       |                    | 10 Calendar Days   |                         |

**NOTE:** Protocol specific exceptions to expedited reporting of serious adverse events are found in the Specific Protocol Exceptions to Expedited Reporting (SPEER) portion of the CAEPR

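### Section 7.1.2 allows atezolizumab rechallenge after myasthenia gravis or Guillain-Barré syndrome, Section 7.3 forbids it, and nothing says which prevails

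*Combined protocol and SAP*

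**What the plan says.** In Section 7.1.2, the neurologic disorders table has one row for myasthenia gravis and Guillain-Barré syndrome at any grade. It calls for permanent discontinuation of atezolizumab and neurologist referral. On steroids it says only "Consider initiation of corticosteroids equivalent to" 1–2 mg/kg/day prednisone. The discontinuation instruction carries marker c, and footnote c reads "Resumption of atezolizumab may be considered in patients who are deriving benefit and have fully recovered from the immune-mediated event". The decision rests on the investigator's documented assessment of benefit and risk.

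In Section 7.3, the row for the same two events, all grades, also calls for permanent discontinuation and adds "Patient may not resume treatment, regardless of benefit". The triplet column repeats the bar and names all three agents. Both columns end by pointing to Section 7.1.2 for further instructions.

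Three other provisions bear on a restart:
- Section 7.1.1: "Monotherapy with atezolizumab or CDX-1127 (varlilumab) alone is not permitted". The same section applies the 7.1.2 guidance to atezolizumab and varlilumab as a single unit.
- Section 9.5.1: "Prior to re-initiating treatment in a subject with a dosing interruption lasting" more than 6 weeks, the Principal Investigator must be consulted.
- Section 10.3: serious events must be reported "whether or not they are considered related to the investigational agent(s)/intervention", and expedited reports go automatically to the Principal Investigator.

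**The concern.** The two rows cover the same events over the same grades, so neither can be read as a special case of the other. Footnote c makes benefit a condition for restarting, whereas 7.3 makes benefit irrelevant. The cross-reference in 7.3 also leads a careful reader straight to the permissive footnote.

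What is at stake is a dosing rule for two serious neurologic events. Footnote c is looser than 7.3's own rule for Grade 3 hepatic, ocular and pulmonary events, where a restart needs consultation with the Principal Investigator. It also sits oddly beside Section 3.2.17, which excludes anyone with a history of either event at any point. Endpoints, sample size and analyses are not affected.

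**Working it through.** **Side-by-side reading**

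| | Section 7.1.2 | Section 7.3 |
|---|---|---|
| Events and grades | Myasthenia gravis, Guillain-Barré; any grade | Same events; all grades |
| Initial action | Permanently discontinue | Permanently discontinue |
| Later restart | May be considered if benefiting and fully recovered | Barred whatever the benefit |
| Who decides | Investigator, documented | No one; no discretion |
| Agents named | Atezolizumab | Both antibodies; plus cobimetinib in the triplet column |

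**Is there a precedence rule?** Three places come close.
- Section 7.2.2 sends restart decisions to 7.3, but only for Arm A and only when the responsible drug is unclear.
- Section 7.2.1 says 7.3 holds the algorithms for standardising management, but calls them suggested and speaks only of Arm A.
- Section 7.1.1 extends 7.1.2 to both antibodies without ranking it against 7.3.

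None settles the question.

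**How far does the permission reach?** Footnote c names atezolizumab alone, and atezolizumab alone is forbidden. A restart under footnote c therefore depends on the single-unit reading in 7.1.1, which would bring varlilumab back as well. Nothing in 7.1.2 permits cobimetinib to restart after these events. A site that never restarts complies with both sections.

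**Window without required consultation.** Section 9.5.1 sets the threshold at 6 weeks = 42 days. If steroids are given, 7.1.2 requires a taper of at least one month (about 30 days) before resumption. So 42 − 30 = about 12 days: the taper must start within about 12 days of the interruption for a restart to fall inside the window. Steroids are only to be considered, so a course without them is not bound by this.

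**Expected number of patients.** The plan gives no figure to reproduce. Let p be the combined rate of the two events and b the chance that a patient is benefiting, with independence assumed. Expected patients = E[N] × p × b.
- Section 9.2: 18 patients per arm in stage 1, 14 more if at least one responds; response rates of 5% and 20%, used for b.
- p is an assumption: 0.1% to 1%. The atezolizumab list in 10.1.1.1 says only that each event is rare but serious, below 3%.
- Probability of stopping an arm at stage 1: 0.95^18 = 0.397 at a 5% response rate (the plan gives 0.4); 0.80^18 = 0.018 at 20%.
- E[N], two arms: 2 × (18 + 14 × (1 − 0.397)) = 52.9; 2 × (18 + 14 × (1 − 0.018)) = 63.5.
- Low: 52.9 × 0.001 × 0.05 = 0.0026.
- High: 63.5 × 0.01 × 0.20 = 0.127.
- With no early stopping (N = 64): 64 × 0.001 × 0.05 = 0.0032 to 64 × 0.01 × 0.20 = 0.128.
- At the listed ceiling, 3% for each event and no overlap (6%): 63.5 × 0.06 × 0.20 = 0.76.

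Requiring full recovery lowers these figures; counting stable disease as benefit raises them.

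**The case against.** The best opposing case is that the protocol already shows which rule it means. In the neuropathy row, 7.3 gives no rule of its own and only refers to 7.1.2. In the myasthenia gravis/Guillain-Barré row the same reference follows an express bar, so the further instructions are naturally the referral and steroid guidance. The bar is also the stricter and regimen-specific text. Section 9.5.1 lists Grade 3 neurologic toxicity and, with exceptions, Grade 4 events as unacceptable toxicities. Section 6.4 ends therapy for unacceptable toxicity, and 7.1.1 requires permanent discontinuation for life-threatening immune events. On this view marker c is an editorial leftover and the practical gap is mainly Grade 1–2 events. A further objection is that the assumed event rate has no source in the documents.

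Much of this stands as evidence of intent, but it does not remove the conflict. The 9.5.1 list defines events for the run-in stopping rule; it is not a general rule on restarting. Permanent discontinuation does not settle the matter either, since footnote c is attached to exactly that instruction. Marker c also cannot be dismissed as boilerplate, because the Grade 2 and Grade 3–4 myelitis rows in 7.1.2 require permanent discontinuation without it. The reports sent under 10.3 tell the Principal Investigator of the event but do not require approval of a restart. The 9.5.1 consultation requirement does narrow the gap, although it stands within the run-in list. If it were read as limited to the run-in, the gap would be wider.

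The point about the event rate is fair. The range is illustrative, and the contradiction does not depend on it.

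**Conclusion.** The inconsistency is real and stands in the current text: one section permits a restart that the other forbids, with no stated order between them. It affects one table row. Under the assumed 0.1% to 1% combined rate, with response as the proxy for benefit and independence between the two, it would concern about 0.003 to 0.13 patients. Even at the listed ceiling for both events the expectation is below one. The exposure is mainly a restart after an interruption of 6 weeks or less, where footnote c calls for no consultation. Section 7.3 is very likely the intended rule, but that is an inference. Severity is minor: a safety instruction should be made unambiguous, and no design or analysis quantity changes.

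**What to change.** First have the sponsor's safety physician confirm that Section 7.3 is the intended rule. Then, in the 7.1.2 row for myasthenia gravis and Guillain-Barré syndrome, delete marker c and add "Patient may not resume treatment, regardless of benefit", with a pointer to 7.3.

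Leave marker c on the neuropathy rows, where 7.3 sets no bar. Keep the 7.3 reference to 7.1.2, because the referral and steroid guidance for these events is found only there.

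This is a one-line amendment with no statistical cost. A recovered patient who had been benefiting would lose the investigator-led rechallenge option, but 7.3 already withholds it.

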## 7.2 Cobimetinib plus Atezolizumab and CDX-1127 (varlilumab) (Treatment Arm A patients only)

### 7.2.1 Recommended Cobimetinib Dose Modifications

In order to standardize the management of AEs, suggested treatment management algorithms for adverse events of particular concern for cobimetinib plus atezolizumab & CDX-1127 (varlilumab) are included in Section 7.3. The following general dose modifications table for cobimetinib is for AEs not specified in the subsequent tables.

| Grade (CTCAE) a  | Recommended Cobimetinib Dose   |
|---|--|
| Grade 1 or Grade 2 (tolerable)  | No dose reduction. Maintain cobimetinib at a dose of 60 mg QD (3 tablets)            |
| Grade 2 (intolerable) or Grade 3 b or 4 (any)
First appearance | Interrupt treatment until Grade $\leq 1$ , restart treatment at 40 mg QD (2 tablets) |
| Second appearance  | Interrupt treatment until Grade $\leq 1$ , restart treatment at 20 mg QD (1 tablet)  |
| Third appearance   | Consider permanent discontinuation   |

CTCAE = Common Terminology Criteria for Adverse Events; NCI = National Cancer Institute; QD = once daily.

a The intensity of clinical adverse events graded by NCI CTCAE v5.0.

b An exception to this is for Grade 3 anemia, without presence of hemorrhage and/or hemolytic process. In this case, participants can be treated with transfusions as needed in order to improve to grade 2 or better and do not require treatment interruption or dose

reduction. If recurrent transfusions are needed, treating provider can consider dose reduction.

Toxicities will be evaluated using NCI CTCAE v5.0. If toxicity occurs, the toxicity will be graded and appropriate supportive care treatment will be administered to decrease symptoms.

Generally, in the case of Grade 4 hematologic or Grade 3 to 4 non-hematologic toxicity (except for Grade 3 skin cancer, squamous or basal cell type), treatment with cobimetinib should be interrupted until recovery to baseline or Grade 1 and then resumed at one dose level reduction. Below is a table for cobimetinib dosing upon dose modification:

| Dose level | Dose                             |
|------------|----------------------------------|
| 0          | 60 mg QD 21 days out of 28 days  |
| (-1)       | 40 mg QD, 21 days out of 28 days |
| (-2)       | 20 mg QD, 21 days out of 28 days |

Up to two dose reductions of cobimetinib will be allowed as follows: 40 mg PO daily and then 20 mg PO daily for 21 days of a 28-day cycle. In the case of recurrent toxicity after two dose reductions, cobimetinib should be discontinued

#### 7.2.2 Management of Cobimetinib plus Atezolizumab and CDX-1127 (varlilumab)–Associated Adverse Events of particular concern (Treatment Arm A)

Due to the triplet combination acting through a range of mechanisms with potential overlapping and also distinct adverse events (AE), patients who experience intolerance or adverse events should be carefully evaluated to examine whether the AE can attributable to one of the two classes of therapies: 1) targeted therapy (cobimetinib); 2) immunotherapy [Atezolizumab and CDX-1127 (varlilumab)]. For example, a patient removed from cobimetinib therapy after developing retinal vein occlusion may continue on with their Atezolizumab and CDX-1127 (varlilumab) combination. If there is ambiguity regarding the responsible drug/class of drug, all three agents should be held/discontinued with special consideration for full/partial regimen resumption as indicated by management guidelines detailed in section 7.3.

Below are recommended management of specific adverse events of particular concern with the triplet combination therapy are provided here.

